7.1.8. Medical Emergencies

Medical emergencies must be reported to the individual identified in the Clinical Study Personnel Contact Information section of this protocol.

Equipment, supplies, and properly skilled medical personnel must be accessible for an adverse event requiring immediate treatment. Any dose of study drug (whether the investigational product, reference therapy, or a placebo), whether taken intentionally or unintentionally, in excess of that prescribed must be immediately reported to the Sponsor. When the identification of the study drug must be known, the investigator must follow the procedures outlined in Section [3.5](#).

7.1.9. Protocol Deviations Because of an Adverse Event

If a patient experiences an adverse event or medical emergency, departures from the protocol may be allowed on a case-by-case basis. After stabilization and/or treatment has been administered to ensure patient safety, the investigator or other physician in attendance must contact the individual identified in the Clinical Study Personnel Contact Information section of this protocol as soon as possible to discuss the situation. The investigator, in consultation with the Sponsor, will decide whether the patient should continue to participate in the study. Any departures from the protocol because of adverse events must be noted on the CRF and in source documents, along with the reason for such departures.

7.2. Pregnancy

All pregnancies (pregnancies of women participating in the study and female partners of men participating in the study) that occur during the study, or within 30 days of completion of the study, are to be reported immediately to the individual identified in the Clinical Study Personnel Contact Information section of this protocol, and the investigator must provide the LSO with the Clinical Trial pregnancy form. The process for reporting a pregnancy is the same as that for reporting a serious adverse event (see Section [7.1.5.3](#)).

Any patient becoming pregnant during the study will be withdrawn from study drug treatment. All patients (or female partners of male patients) who become pregnant will be monitored to the completion or termination of the pregnancy. If the pregnancy continues to term, the outcome (health of the infant up to 8 weeks of age), details of birth, and presence or absence of any birth defect, congenital abnormalities, or maternal and newborn complications will be reported to the Sponsor. Any complication of pregnancy will be reported as an adverse event or serious adverse event, as appropriate.

If the pregnancy does not continue to term, 1 of the following actions will be taken:

- For a spontaneous abortion, report as a serious adverse event.
- For an elective abortion due to developmental anomalies, report as a serious adverse event.

- For an elective abortion **not** due to developmental anomalies, report on the pregnancy form.

7.3. Clinical Laboratory Tests

All clinical laboratory test results outside of the reference range will be interpreted by the investigator as belonging to 1 of the following categories:

- abnormal but not a clinically significant worsening
- abnormal and a clinically significant worsening

A laboratory test result that has significantly worsened (according to medical judgment) from the baseline result will be recorded on the source documentation, transcribed onto the CRF as an adverse event, and monitored as described in Section 7.1.2. An adverse event includes a laboratory or diagnostic test abnormality (once confirmed by repeat testing) that results in the withdrawal of the patient from the study, the temporary or permanent cessation of treatment with study drug, or medical treatment or further diagnostic work-up.

Clinical laboratory tests (serum chemistry and hematology) and urinalysis will be performed at the time points indicated in [Table 1](#). The clinical laboratory tests will be performed using a central laboratory, with more details provided in the Laboratory Procedures Manual for this study. The urinalysis will be done macroscopically at the study site with a dipstick provided by the central laboratory. If any portion of the dipstick is positive, the urine sample will be sent to the central laboratory for microscopic evaluation. The dipstick results will be recorded in the CRF. Specific laboratory tests to be performed are listed below.

7.3.1. Serum Chemistry

The following serum chemistry tests will be performed:

- calcium
- phosphorus
- sodium
- potassium
- chloride
- bicarbonate or carbon dioxide
- glucose
- blood urea nitrogen (BUN)
- creatinine
- cholesterol
- uric acid
- ALT
- AST

- lactic dehydrogenase (LDH)
- gamma-glutamyl transpeptidase (GGT)
- alkaline phosphatase
- creatine phosphokinase
- total protein
- albumin
- total bilirubin
- direct bilirubin
- indirect bilirubin

7.3.2. Hematology

The following hematology tests will be performed:

- hemoglobin
- hematocrit
- red blood cell (RBC) count
- platelet count
- absolute neutrophil count
- white blood cell (WBC) count and differential count
 - polymorphonuclear leukocytes (neutrophils)
 - lymphocytes
 - eosinophils
 - monocytes
 - basophils
 - atypical lymphocytes

7.3.3. Urinalysis

Urinalysis will include testing for the following:

- protein
- glucose
- ketones
- blood (hemoglobin)
- pH
- specific gravity

- microscopic, as needed
 - bacteria
 - RBCs
 - WBCs
 - casts
 - crystals

7.3.4. Other Clinical Laboratory Tests

Other clinical laboratory tests will be performed to ensure the safety of the patients but will not be used to assess the safety of the study drug.

7.3.4.1. Pregnancy Tests

Urine pregnancy tests will be performed at the study site (with test kits provided by a central laboratory) for all women of child-bearing potential at screening (visit 1), randomization (visit 3, day 1), visit 4 (day 15 \pm 1, week 2), visit 5 (day 29, week 4), and at the follow-up/ET visit (visit 6, day 57 \pm 3). Any patient who becomes pregnant during the study will be withdrawn. Procedures for reporting the pregnancy are provided in Section 7.2.

7.3.4.2. Urine Drug Screen

A urine drug screen will be performed at the time points indicated in Table 1. The urine drug screen includes a means to detect the presence of drugs prohibited according to the protocol, including cannabinoids, cocaine, amphetamines, barbiturates, benzodiazepine, and opiates. If a parameter noted above cannot be tested using urine, an alternative matrix (eg, serum) may be considered acceptable. The Sponsor's medical expert must be made aware in advance of, and provide approval for, drug screen parameters to which this will apply. A positive result for any of the above drugs or their metabolites, without medical explanation, will preclude the patient from enrollment or continued participation in the study.

7.4. Vital Signs

Vital signs will be measured at the time points indicated in Table 1. Vital signs include the following:

- heart rate
- respiration rate
- body temperature
- blood pressure

Before pulse and blood pressure are measured, the patient must be in a supine or seated position and resting for at least 5 minutes. (The same position and arm should be used each time vital signs are measured for a given patient.) For any abnormal vital sign finding, the measurement should be repeated as soon as possible. Any vital sign value that is judged by the investigator as a clinically significant change (worsening) from a baseline value will be considered an adverse

event, recorded on the source documentation and transcribed onto the CRF, and monitored as described in Section 7.1.2.

7.5. **Electrocardiography**

A 12-lead ECG will be conducted as triplicate tracings taken at least 1 minute apart (with an upper limit of 5 minutes apart) at the time points indicated in Table 1. To determine eligibility based upon numerical exclusion criteria of cardiac intervals, the investigator will use the mean values of 3 ECGs. A qualified physician at a central diagnostic center will be responsible for interpreting the ECG. Any ECG finding that is judged by the investigator as a clinically significant change (worsening) compared with a baseline value will be considered an adverse event, recorded on the source documentation and transcribed onto the CRF, and monitored as described in Section 7.1.2.

7.6. **Physical Examinations**

Physical examinations, including height (to be obtained at the screening visit only) and weight (screening and follow-up/ET visits only) will be performed at the time points indicated in Table 1. Any physical examination finding that is judged by the investigator as a clinically significant change (worsening) compared with a baseline value will be considered an adverse event, recorded on the CRF, and monitored as described in Section 7.1.2.

7.7. **Other Safety Measures and Variables: Concomitant Therapy or Medication**

Concomitant therapy or medication usage will be monitored throughout the study. Details of prohibited medications are found in Section 5.3.

7.8. **Methods and Timing of Assessing, Recording, and Analyzing Safety Data**

Methods and timing of assessing safety data are discussed in Section 3.11. Procedures for recording safety data are discussed in Section 13.1 and methods of analyses are discussed in Section 9.8.2.

7.9. **Dermal Irritation Evaluation**

Dermal irritation will be evaluated at the time points indicated in Table 1 using the scale below (FDA 1999):

- 0 = no evidence of irritation
- 1 = minimal erythema (barely perceptible)
- 2 = definite erythema, readily visible; minimal edema or minimal papular response
- 3 = erythema and papules
- 4 = definite edema
- 5 = erythema, edema, and papules

- 6 = vesicular eruption
- 7 = strong reaction spreading beyond test site

8. ASSESSMENT OF PHARMACOKINETICS / PHARMACODYNAMICS / PHARMACOGENOMICS

8.1. Pharmacokinetic Variables

Samples (plasma) will be analyzed for TV-45070 using an appropriate validated method.

The dates and times of study drug administration and the date and time of each pharmacokinetic sample must be well documented on the source documentation and transcribed onto the CRF.

Samples will be collected into K₂EDTA VACUTAINER® (Becton, Dickinson and Company) tubes, inverted slowly 6 to 8 times to mix the contents, and placed on ice (0°C to 5°C). Blood samples will be centrifuged (1500 × g, approximately 10 minutes, 0°C to 5°C) within 1 hour after sampling. If a refrigerated centrifuge is not available, samples should be chilled before centrifugation. As needed, other measures should be taken to prevent samples from heating significantly during centrifugation. Separated plasma will be transferred in approximately equal portions into 2 opaque, labeled, polypropylene tubes (sets A and B).

Sample labels should include the study number, patient identification number, visit number, nominal collection time, set (A or B), and indication that they are pharmacokinetic samples. Plasma samples will be placed on ice (0°C to 5°C) in an upright position until they are frozen at -70°C within 1 hour of centrifugation.

Plasma samples for all patients will be shipped from the study site to the central laboratory upon the Sponsor's request and will be shipped in batch shipments to the central laboratory designated in the Study Laboratory Manual. Samples will be stored in an upright position at -70°C until assayed. The laboratory will be notified before the shipment of the samples and will be sent the shipping information when the samples are shipped.

Set A samples will be transported, frozen with sufficient dry ice for 4 days, by next day courier to Teva Pharmaceutical Works P.Ltd.Co. as described in the Study Laboratory Manual.

Set B samples will be shipped and stored as described in the Study Laboratory Manual.

Sample shipments should be sent no later in the week than Wednesday morning for next day delivery. Samples are not to arrive on the weekend.

Further details for sample collecting, handling, shipping, and storage are provided in the Study Laboratory Manual.

8.2. Pharmacodynamic Variables

Pharmacodynamic endpoints assessed during the study are the secondary efficacy endpoints change from baseline in maximal intensity of patients' brush-evoked allodynia and change from baseline in maximal intensity of patients' punctate-evoked hyperalgesia.

8.3. Pharmacogenomic Variables

It is recognized that genomic variation within the population can be an important contributory factor to inter-individual differences in drug response. Pharmacogenomic analyses investigate

the association between genetic sequence polymorphisms and/or gene expression signatures and clinical response to a certain therapeutic intervention. Pharmacogenomic results may help explain inter-individual variability and subsequently identify population subgroups that respond differently to the drug. Furthermore, regulatory guidance and white papers indicate that pharmacogenomic analyses employing DNA collected from all study participants may support investigation of unexpected adverse events.

The objectives of the pharmacogenomic analyses in this study are as follows:

- To genotype the underlying R1150W polymorphism in the *SCN9A* gene so as to stratify patients according to R1150W polymorphism status (homozygous minor allele [positive, AA], heterozygous [positive, AG], and homozygous common allele [negative, GG]) in the randomization
- [REDACTED]
- [REDACTED]
- To genotype polymorphisms of the *CYP3A4* and *CYP2C19* genes as potential covariates in the population pharmacokinetic analysis

Individual patients will be genotyped for the R1150W polymorphism for randomization allocation purposes. Pharmacogenomic samples will be stored for a period of up to 15 years after the last patient last visit in the study and then destroyed. [REDACTED]

Pharmacogenomic assessment will be performed using blood samples of 12 mL total volume, collected in 2 K₃EDTA Vacutainer plastic tubes for pharmacogenomic analysis (1 sample will be used for the R1150W randomization test and the other for further pharmacogenomic analyses). Pharmacogenomic samples will be collected from all patients at the screening visit (visit 1) because randomization will be stratified based on R1150W polymorphism status. The samples may also be examined for other sequence variations in the *SCN9A* gene region and/or other genes. [REDACTED]

[REDACTED] A patient's refusal to have this blood sample taken will exclude him/her from participation in this study.

Pharmacogenomic samples will be sent to the central laboratory within 72 hours after collection. Further details for sample collecting, handling, shipping, and storage will be provided in the Study Laboratory Manual.

The R1150W polymorphism test will be done at the central laboratory, a Clinical Laboratory Improvement Amendments-certified laboratory, and the exact genotyping assay will be selected in discussion with the laboratory staff. The laboratory for the testing of other genetic variations will be selected after the start of this study (TV45070-CNS-20013) and will be performed if and when required. The laboratory for these other analyses will be selected according to the nature of the analyses.

9. STATISTICS

9.1. Study Design and Randomization

This is a double-blind, randomized, placebo-controlled, parallel-group study to evaluate the efficacy and safety of TV-45070 treatment in patients with PHN. Patients will be randomly assigned to receive treatment with 4% w/w TV-45070 ointment, 8% w/w TV-45070 ointment, or matching placebo ointment in a 1:1:1 ratio. Randomization will be as described in Section 3.4.

9.2. Sample Size and Power Considerations

In prior studies of gabapentin or pregabalin treatment of PHN, the difference in mean pain scores between active- and placebo-treated groups ranged from 1.0 (Rice et al 2001) to 1.3 (Dworkin et al 2003). For this decision-making, proof-of-concept study, it is reasonable to use a conservative estimate of 1.0. If we assume a standard deviation of 2.35, a sample size of 88 per arm (a total of 264 patients) would be needed to provide 80% power with a 2-sided test at 5% significance level to detect a 1.0-point difference. Assuming an approximately 20% dropout rate, 110 patients per arm (a total of 330 patients) will be randomly assigned to each treatment group. During the study, the ultimate sample size may be adjusted on the basis of the actual dropout rate.

9.3. Analysis Sets/Populations

9.3.1. Intent-to-Treat Population

The intent-to-treat (ITT) population will include all randomized patients. In this population, treatment will be assigned based on the treatment to which patients were randomized, regardless of which treatment they actually received.

9.3.2. Safety Population

The safety population will include all randomized patients who receive at least 1 dose of study drug. In this population, treatment will be assigned based upon the treatment patients actually receive, regardless of the treatment to which they were randomized.

9.3.3. Full Analysis Set

The full analysis set (FAS), defined as all patients in the ITT population (all patients randomly assigned to treatment) who receive at least 1 dose of study drug and have at least 1 post-baseline efficacy assessment, will be used for all efficacy analyses. Summaries will be presented by treatment group. The FAS will serve as the primary analysis set for efficacy analyses.

9.3.4. Per Protocol Population

The PP population will include all subjects in the FAS who have not had major protocol deviations (ie, protocol violations). Protocol violations will be determined before unblinding. The PP Population will serve as the supportive population for efficacy analyses.

9.3.5. Additional Analysis Sets

The population pharmacokinetic analysis set will include all patients in the pharmacokinetic subset who had at least 1 pharmacokinetic plasma sample analyzed for TV-45070.

9.4. Data Handling Conventions

For all variables, only the observed data from the patients will be used in the by-visit summaries. Data imputation rule(s) will be detailed in the Statistical Analysis Plan.

9.5. Study Population

The ITT population (see Section 9.3.1) will be used for all study population summaries unless otherwise noted. Summaries will be presented by treatment group and for all patients.

9.5.1. Patient Disposition

Data from patients screened, patients screened but not randomized and reason not randomized, patients who are randomized/enrolled, patients randomized/enrolled but not treated (and reason), patients in the safety set and FAS, patients who complete the study, and patients who withdraw from the study will be summarized using descriptive statistics. Data from patients who withdraw from the study will also be summarized by reason for withdrawal using descriptive statistics.

9.5.2. Demographic and Baseline Characteristics

Patient demographic and baseline characteristics, including medical history, prior medications, and ECG findings, will be examined to assess the comparability of the treatment groups and will be summarized using descriptive statistics. For continuous variables, descriptive statistics (number [n], mean, standard deviation, standard error, median, minimum, and maximum) will be provided. For categorical variables, patient counts and percentages will be provided. Categories for missing data will be presented if necessary.

The categorical variables of patient sex and race will be summarized using descriptive statistics for each variable category. Missing categories will be presented if necessary. Treatment groups will be compared for all categorical variables using a Pearson’s chi-square (or Fisher’s exact test if cell sizes are too small).

9.6. Efficacy Analysis

The primary, secondary, and exploratory efficacy variables and endpoints are described in Section 3.3.

9.6.1. Planned Method of Analysis

The FAS (see Section 9.3.3) will serve as the primary analysis set for all efficacy analyses. The PP population will be the supportive population for efficacy analyses.

9.6.1.1. Primary Efficacy Analysis

The primary efficacy variable, change from baseline to week 4 in the weekly average of the daily average NRS scores, will be analyzed using a Mixed Model Repeated Measures (MMRM) model with change from baseline in the weekly average of the daily average NRS scores at weeks 2 and

4 as the dependent variable; visit in weeks, treatment, and treatment by visit interaction as fixed factors; baseline weekly average of the daily average NRS scores as covariate; and patient as random effect. The unstructured covariance matrix for repeated observations within patients will be used. The primary treatment comparison will be conducted at week 4 in this model. All tests will be 2-sided at a significance level of 0.05. More details will be provided in the Statistical Analysis Plan.

9.6.1.2. Sensitivity Analysis

Sensitivity analysis on the primary efficacy variable, while taking discontinuation reason and rescue medication usage into consideration, may be performed.

9.6.1.3. Secondary Efficacy Analysis

The continuous secondary efficacy variables will be analyzed in a similar way as the primary efficacy variable.

The percentages of patients with $\geq 30\%$ and $\geq 50\%$ improvement from baseline in weekly average NRS scores at week 4 will be summarized using descriptive statistics. The time to reach $\geq 30\%$ improvement in weekly average NRS scores from baseline will also be summarized using descriptive statistics.

PGIC scores will be analyzed using a MMRM model with week, treatment, and treatment by week interaction as fixed factors and patient as a random factor. The unstructured covariance matrix for repeated observations within patients will be used.

NePIQoL score will be analyzed using an analysis of covariance (ANCOVA) model with effects due to baseline and treatment, imputing missing data via last observation carried forward (LOCF).

9.6.1.4. Exploratory Efficacy Analysis

[REDACTED]

9.7. Multiple Comparisons and Multiplicity

This is a Phase 2 study, and there is no plan to adjust for multiplicity.

9.8. Safety Variables and Analysis

9.8.1. Safety Variables

The overall safety and tolerability of topical TV-45070 (4% and 8% w/w ointment) treatment will be assessed throughout the study by evaluating adverse events and the following additional safety variables at the time points specified in Section 3.11:

- clinical laboratory tests
- vital signs
- physical examination
- dermal irritation
- 12-lead ECGs
- concomitant therapy or medication usage

9.8.2. Safety Analysis

All adverse events will be coded using the Medical Dictionary for Regulatory Activities (MedDRA). Each patient will be counted only once in each preferred term or system organ class (SOC) category for the analyses of safety. Summaries will be presented for all adverse events (overall and by severity), adverse events determined by the investigator to be related to study treatment (ie, reasonable possibility; see Section 7.1.4) (adverse events defined as related or with missing relationship will be summarized overall and by severity), serious adverse events, and adverse events causing withdrawal from the study. Summaries will be presented by treatment group and for all patients. Patient listings of serious adverse events and adverse events leading to withdrawal will be presented.

Changes in laboratory and vital signs measurement data will be summarized descriptively. All values will be compared with prespecified boundaries to identify potentially clinically significant changes or values, and such values will be listed.

The use of concomitant medications will be summarized by therapeutic class using descriptive statistics. Concomitant medications will include all medications taken while the patient is treated with study drug.

For continuous variables, descriptive statistics (n, mean, standard deviation, standard error, median, minimum, and maximum) will be provided for actual values and changes from baseline to each time point. For categorical variables, patient counts and percentages will be provided. Descriptive summaries of serious adverse events, patient withdrawals due to adverse events, and potentially clinically significant abnormal values (clinical laboratory or vital signs) based on predefined criteria will also be provided.

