## **4. GENERAL ISSUES FOR DATA ANALYSIS**

### **4.1. General**

Descriptive statistics for continuous variables include n, mean, standard deviation (SD), standard error of the mean (SE), median, minimum, and maximum. If inferential statistics are computed, it will also include least square mean and standard error of the least square mean, 95% confidence interval, and p-value, unless otherwise specified. Descriptive statistics for categorical variables include patient counts and percentages.

Summaries of potentially clinically significant abnormal values will include all postbaseline values (including scheduled, unscheduled, and early termination visits).

The last visit for efficacy and safety analyses and summaries is the last observed postbaseline data up to Week 4 visit.

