#### 7.5. Clinical Laboratory Tests

Summary statistics for chemistry, hematology, and urinalysis laboratory tests will be presented at baseline, week 2, week 4, last visit, and follow-up. Laboratory tests results and changes from baseline to each visit and last visit will be summarized using descriptive statistics. Shifts (below, within, and above the normal range) from baseline to each visit and last visit will be summarized using patient counts. The incidence of potentially clinically significant abnormal results will be summarized for laboratory data using descriptive statistics with the criteria specified in [Table 3](#).

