**Table 3: Criteria for Potentially Clinically Significant Abnormal Laboratory Values**

Test	Criterion value
Serum chemistry	
Alanine aminotransferase (ALT)	$\geq 3 \times$ ULN
Aspartate aminotransferase (AST)	$\geq 3 \times$ ULN
Alkaline phosphatase	$\geq 3 \times$ ULN
Gamma-glutamyl transpeptidase (GGT)	$\geq 3 \times$ ULN
Lactate dehydrogenase (LDH)	$\geq 3 \times$ ULN
Blood urea nitrogen (BUN)	$\geq 10.71$ mmol/L
Creatinine	$\geq 177$ $\mu$ mol/L
Uric acid	
Men	$\geq 625$ $\mu$ mol/L
Women	$\geq 506$ $\mu$ mol/L
Bilirubin (total)	$\geq 34.2$ $\mu$ mol/L
Hematology	
Hematocrit	
Men	$< 0.37$ L/L
Women	$< 0.32$ L/L
Hemoglobin	
Men	$\leq 115$ g/L

Test	Criterion value
Women	$\leq 95$ g/L
White blood cell (WBC) counts	$\leq 3 \times 10^9$ /L $\geq 20 \times 10^9$ /L
Eosinophils	$\geq 10\%$
Absolute neutrophil counts (ANC)	$\leq 1 \times 10^9$ /L
Platelet counts	$\leq 75 \times 10^9$ /L $\geq 700 \times 10^9$ /L
Urinalysis	
Blood (HGB)	$\geq 2$ unit increase from baseline
Glucose	$\geq 2$ unit increase from baseline
Ketones	$\geq 2$ unit increase from baseline
Total protein	$\geq 2$ unit increase from baseline

ULN=upper limit of normal range.

Listings for potentially clinically significant abnormal laboratory data will be presented.

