## 7.6. Vital Signs

Summary statistics for vital signs will be presented at baseline, weeks 2, 4, last visit, and follow-up. Vital signs values and changes from baseline to each visit and last visit will be summarized using descriptive statistics. The incidence of potentially clinically significant abnormal values will be summarized for selected vital signs using descriptive statistics.

**Table 4** specifies the criteria for identifying vital signs as potentially clinically significant abnormal. Note that in order to be identified as potentially clinically significant abnormal, a value would need to meet both conditions below: ie, have a value beyond the criterion value and a change of at least the magnitude specified in the change from baseline column.

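### Chemistry and haematology results are flagged as potentially clinically significant on an absolute limit alone, so an abnormality that was present before dosing and persists counts towards the on-treatment incidence (minor)

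*Protocol*

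**What the plan says.** The protocol sets no limits itself. Section 9.8.2 says that descriptive summaries of "potentially clinically significant abnormal values (clinical laboratory or vital signs) based on predefined criteria will also be provided", and its wording allows either values or changes to be flagged. The operative rule is in the SAP:

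- **SAP 7.5:** "The incidence of potentially clinically significant abnormal results will be summarized for laboratory data using descriptive statistics with the criteria specified in" Table 3, which is titled "Criteria for Potentially Clinically Significant Abnormal Laboratory Values".
- **Table 3, chemistry and haematology:** limits only. Examples are BUN ≥10.71 mmol/L, creatinine ≥177 µmol/L, ALT ≥3 × ULN, haemoglobin ≤115 g/L in men and eosinophils ≥10%. No row has a baseline or change condition.
- **Table 3, urinalysis:** each row requires a 2-"unit increase from baseline" or more.
- **SAP 7.6 and Table 4, vital signs:** "a value would need to meet both conditions below", that is, "have a value beyond the criterion value and a change of at least the magnitude specified in the change from baseline column".
- **SAP 4.1, which values enter:** "Summaries of potentially clinically significant abnormal values will include all postbaseline values (including scheduled, unscheduled, and early termination visits".
- **SAP 4.2:** defines a laboratory baseline, the last non-missing value before the first dose.

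Nothing in SAP 7.5, Table 3 or the list of tables removes or separates patients who already met a limit at baseline.

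**The concern.** A man with haemoglobin 112 g/L before dosing and 112 g/L at week 4 is flagged, although nothing has changed. A man who falls from 140 to 112 g/L is flagged in the same way, and Table 15.3.17 cannot tell the two apart.

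Eligibility does not prevent this. Exclusion i requires an uncontrolled disorder that may endanger the patient, and exclusion x rests on the investigator's opinion of the laboratory findings. Neither uses a numeric chemistry or haematology limit. Protocol 1.1 notes that most people with PHN are elderly, so stable renal or haematological abnormalities at entry are plausible, though the documents give no prevalence.

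Safety compared with placebo is a stated secondary objective, and Tables 15.3.16 and 15.3.17 are the arm-level tables of laboratory outliers. Pre-existing cases add a similar number to each arm on average. That pulls the rates together in relative terms and adds noise. With no test planned, readers will judge these tables by eye.

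**Working it through.** **The plan's own figure.** The documents give no laboratory rates, so the only figure to reproduce is the arm size. For SD 2.35, difference 1.0, two-sided 5% and 80% power, the normal approximation gives 87 per arm and the t-test version 87.7, so 88. Then 88 / 0.80 = 110 randomized per arm. This reproduces and is unaffected by the point. I use 110 below.

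**Assumed inputs (none are in the documents).** New-onset rate p = 2% on placebo and 10% on an active arm. Baseline prevalence b from 1% to 10%. Persistence s = the proportion of baseline abnormalities that meet the limit again after baseline, equal across arms, at 1 or 0.5.

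**Formulas.**
- Flagged rate under the SAP rule: q = b·s + (1 − b)·p.
- Risk difference: q₁ − q₀ = (1 − b)(p₁ − p₀). The term b·s cancels.
- Risk ratio: q₁/q₀, which moves towards 1 as b·s grows.
- Rule restricted to patients not meeting the limit at baseline: rates p₀ and p₁, so difference 8.0 points and ratio 5.0 at every b.

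**Central case, b = 5%, s = 1.**
- Placebo: 0.05 + 0.95 × 0.02 = 0.069, or 7.6 of 110.
- Active: 0.05 + 0.95 × 0.10 = 0.145, or 16.0 of 110.
- Ratio 0.145 / 0.069 = 2.1. Difference 7.6 points.
- Pre-existing cases per arm: 110 × 0.05 = 5.5, which is 5.5 / 7.6 = 72% of the placebo count.

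**Range.** The last two columns give the power of an illustrative two-sided 5% Fisher exact test. The plan has no such test; it serves only as a measure of signal against noise.

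| b | s | Difference (points) | Ratio | SAP rule | New cases only |
|---|---|---|---|---|---|
| 1% | 1 | 7.9 | 3.7 | 57% | 64% |
| 3% | 1 | 7.8 | 2.6 | 45% | 63% |
| 3% | 0.5 | 7.8 | 3.3 | 52% | 63% |
| 5% | 1 | 7.6 | 2.1 | 37% | 61% |
| 5% | 0.5 | 7.6 | 2.7 | 46% | 61% |
| 10% | 1 | 7.2 | 1.6 | 25% | 58% |
| 10% | 0.5 | 7.2 | 2.1 | 34% | 58% |

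**Chance imbalance.** The between-arm difference in the number of patients abnormal at baseline has SD √(2 × 110 × 0.05 × 0.95) = 3.2 patients at b = 5%. It can push the contrast either way, so it can also create an apparent signal.

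**Do other outputs show new cases by arm?** The shift tables use below, within and above the normal range. An ALT that rises from 1.2 × to 4 × ULN is above at both times and shows no shift. In the outlier table it looks the same as a patient at 4 × ULN throughout. Summaries of mean change do not isolate outliers. Listings allow patient-by-patient checking but give no rate.

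**The case against.** Several points on the other side stand.

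- **Pre-dose values are not themselves counted.** A reader might infer that every abnormality present before the first dose enters the table. SAP 4.1 admits only postbaseline values, so a patient counts only if a later value also meets the limit. Full persistence is an assumption, and at half persistence the loss is smaller.
- **The absolute contrast is nearly intact.** A reader might infer that any drug–placebo difference is washed out. At 5% prevalence 95% of the risk difference remains. The damage is to the ratio and to signal against noise.
- **The prevalences are assumed, and each is for a single test.** Nothing in the documents supports 3% to 10% for rows set at 3 × ULN or for the extreme platelet limits. At 1% the loss is small.
- **No test is planned,** so no power is lost in a formal sense.
- **Baseline is used elsewhere.** Changes from baseline, shift tables and listings are planned, and protocol 7.3 makes a significant worsening from baseline an adverse event. Tables 15.3.16 and 15.3.17 are not the only place where a signal could appear.
- **The word incidence is used loosely.** SAP 5.5 applies it to prior medications, where it can only mean a count of patients.

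What remains is that no planned output gives the rate of new potentially clinically significant chemistry or haematology cases by arm, and that the SAP gives no reason for treating these tests differently from urinalysis and vital signs.

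**Conclusion.** The gap is real and minor. It lies in SAP 7.5 and Table 3, read with SAP 4.1. The protocol sentence only points there and is not itself wrong.

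With equal persistence across arms, the risk difference falls by the factor (1 − b) alone. The ratio can fall materially: from 5.0 to 2.1 in the central case, and to between 3.7 and 1.6 over prevalences of 1% to 10% with full persistence. All these rates are assumptions.

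The documents do not support the stronger inference that the trial would miss a laboratory signal. The tables are descriptive, other baseline-aware outputs exist, and the primary analysis is untouched.

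**What to change.** In SAP 7.5, and in Tables 15.3.16 and 15.3.17:

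1. Count a chemistry or haematology result as an incident case only in a patient whose baseline value did not meet the same criterion. Use those patients as the denominator. Where a test has a lower and an upper limit (white cells, platelets), apply this to each limit separately.
2. Show patients who already met the criterion at baseline in a separate row, with their change from baseline to the worst postbaseline value. A count alone would not do: a patient who goes from 3.1 to 10 × ULN would look the same as one who stays at 3.1.
3. State how patients with no baseline value are handled.

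The limits in Table 3, the urinalysis rows and the vital-sign rule stay as they are. The baseline needed is already defined in SAP 4.2, so no new data are collected. The cost is a short addition to SAP 7.5, a derived flag, one extra row per test and slightly smaller denominators (at 5% prevalence, about 104 of 110 per arm).
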